4.3.2. Primary Analysis for the Primary Endpoint

Pharmacokinetic parameter estimates for mirikizumab will be calculated using standard noncompartmental methods of analysis.

The primary parameters for analysis will be the C_{\max} , $AUC_{(0-\infty)}$, and $AUC_{(0-t_{\text{last}})}$ of mirikizumab. The secondary parameter for analysis will be the t_{\max} of mirikizumab.

The PK parameters will be summarized by treatment and listed. Additionally, the PK parameters will also be summarized by treatment and injection site location.

4.3.2.1. Pharmacokinetic Statistical Methodology

The C_{\max} , $AUC_{(0-\infty)}$, and $AUC_{(0-t_{\text{last}})}$ will be log-transformed and analyzed using a linear fixed-effects model. The model will include mirikizumab administration method ($2 \times 1 \text{ mL}$ as reference, $1 \times 2 \text{ mL}$ as test), injection site location, and weight category stratification as fixed effects. The least squares (LS) mean differences between mirikizumab administration method administrations (across all locations) will be back transformed to present the ratios of geometric LS means and the corresponding 90% confidence interval (CI). Comparisons will be made between the 2 administration methods.

Example SAS Code:

```
proc mixed data=xxxx;  
by parameter;  
class administration location strat_weight;  
model log_pk = administration location strat_weight / residual;  
lsmeans administration / alpha=0.1 cl pdiff;
```

```
lsmeans location / alpha=0.1 cl pdiff;
ods output lsmeans=lsmeans diffs=diffs;
run;
```

The two administration methods will be considered bioequivalent if the 90% CIs of the ratio of geometric LS means fall within 0.800 to 1.250.

In addition, the t_{max} of mirikizumab between the two administration methods will be analyzed using a Wilcoxon rank-sum test. Estimates of the median, the median difference, approximately 90% CIs, and p-values from the Wilcoxon rank-sum test will be reported.

Example SAS code:

```
proc nparlway data = xxx hl(refclass="xx") alpha = 0.1;
by parameter;
class administration;
var pk;
exact wilcoxon hl;
ods output wilcoxontest = Wilcoxon;
ods output HodgesLehmann=hl;
run;
```

Using the same model, the following exploratory comparisons will also be made:

- The 2 administration methods (2×1 mL [Reference] versus 1×2 mL [Test]) compared separately at each injection location (injection location will be removed from the model above)
- The 3 injection locations (arm [Test] versus abdomen [Reference] and thigh [Test] versus abdomen [Reference]) separately for each administration method (2×1 mL [Reference] versus 1×2 mL [Test]) (administration methods will be removed from the model above)

There is no intention for formal statistical analysis in these comparisons but rather to explore potential heterogeneity; therefore, bioequivalence will not be determined based on this exploratory purpose.

Additional PK analyses may be conducted if deemed appropriate.

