1.3. Schedule of Activities (SoA)

Procedure	Screening	Study Day																	Comments
		-1	1	3	5 ±1d	8 ±1d	11 ±1d	15 ±2d	22 ±2d	29 ±2d	36 ±2d	43 ±2d	50 ±2d	57 ±3d	64 ±3d	71 ±3d	ED		
Informed consent	X																		
Medical history and demographics	X																		
Review and confirm I/E criteria	X	X																	
Admission to CRU		X																	
Discharge from CRU			X																Participants may be discharged after completing the 4h safety assessments on D1, or later at the investigator's discretion.
Outpatient visit	X			X	X	X	X	X	X	X		X		X		X	X		
Telephone call											X		X		X				To check on the presence of any AEs and CMs.
Randomization		X	P																Randomization can occur on D-1 or D1; participants will be randomized as described in Section 4.1.
Height, weight, and BMI	X	X														X	X		Only weight will be measured on D-1 and D71 or ED.
Body temperature	X	X	P	X	X	X	X	X	X	X		X		X		X	X		
Physical examination		X	X													X	X		Complete physical examination at either screening or D-1. Symptom-directed examinations and assessments at D71 or ED, and as deemed necessary by the investigator or designee.

Procedure	Screening	Study Day																	Comments
		-35 to -2 days prior to Day 1	-1	1	3	5 ±1d	8 ±1d	11 ±1d	15 ±2d	22 ±2d	29 ±2d	36 ±2d	43 ±2d	50 ±2d	57 ±3d	64 ±3d	71 ±3d	ED	
Vital signs (pulse rate and blood pressure) (sitting) (hours)		X	X	P, 2 to 4					X				X				X	X	D1: 2h to 4h to be conducted at least 2h after the last injection and prior to discharge at approximately 4h postdose. Time points may be added if warranted and agreed upon between Lilly and the investigator.
Hematology, clinical chemistry, urinalysis	X	X	P	X				X		X							X	X	See Section 10.2.
Serology	X																		See Section 10.2.
QuantiFERON®-TB Gold test	X																		See Section 10.2.
Breath or urine ethanol test and urine drug screen	X	X																	May be repeated at additional time points at the discretion of the investigator. See Section 10.2.
FSH (participants who are AFAB only)	X																		See Section 10.2.
Pregnancy test (participants who are AFAB only)	X	X															X	X	Serum at screening and D-1. Urine at D71 or ED. See Section 10.2.
Single 12-lead ECG (supine)	X	X															X	X	May be obtained at additional times, when deemed clinically necessary.
Mirikizumab administration			X																
Mirikizumab PK sample			P	X	X	X	X	X	X	X	X		X		X		X	X	See Section 10.2.

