2.2.4. Pharmacokinetics

Studies in healthy participants and adult participants with UC found that mirikizumab exposure increased proportionally, and that mirikizumab has a half-life of approximately 9.3 days and SC absolute bioavailability of 44%.

Body weight was identified as a covariate on the clearance of mirikizumab and BMI was identified as a covariate on the SC bioavailability of mirikizumab, with participants with higher body weight or BMI having a lower mirikizumab exposure. Although the effect size of weight or BMI is not considered clinically relevant, it represents a potential confounding factor for the bioequivalence evaluation. Therefore, participants will be stratified by weight in the current study.

Citrate-free mirikizumab

In Study AMBV, no statistically significant differences in C_{max} , $AUC(0-\infty)$, and $AUC(0-t_{last})$ were observed following administration of the 200-mg mirikizumab solution formulation and mirikizumab citrate-free solution formulation as 2×1 -mL SC injections into the arms, thighs, or abdomen overall nor at each injection site separately, with the 90% CIs for the ratios of geometric least squares means including unity. There was no statistically significant difference in the median t_{max} of mirikizumab between the formulations.

In Study AMBT, bioequivalence was observed between the 100-mg/mL mirikizumab solution and citrate-free solution using 2×1 -mL SC injections via AI, as assessed by $AUC(0-t_{last})$, $AUC(0-\infty)$, C_{max} , and t_{max} .

In Study AMBY, bioequivalence was observed between the mirikizumab solution and citrate-free mirikizumab SC solution in 1-mL and 2-mL PFS as assessed by $AUC(0-t_{last})$, $AUC(0-\infty)$, and C_{max} .

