4.2. Scientific Rationale for Study Design

Conducting the study in healthy participants mitigates the potential confounding effects of the disease state and concomitant medications in participants. A population of healthy participants is frequently used in the assessment of the PK of both small and large molecules.

Single doses of citrate-free mirikizumab and the PK sampling time points have been selected to generate PK profiles sufficient to fulfill the study objectives.

The mirikizumab citrate-free solution formulation is being investigated as a potential replacement for the mirikizumab solution formulation and has been used in 3 Phase 1 clinical trials (Studies I6T-MC-AMBT, I6T-MC-AMBV, and I6T-MC-AMBY).

Due to the 5-day return of results for the QuantiFERON® TB Gold test, a 35-day screening period has been selected. The extension from the standard 28 days allows investigative sites more flexibility to screen, randomize, and dose a larger number of healthy participants.

Weight will be stratified into 3 categories, administration methods will be randomized, and injection site will be assigned. The number of participants randomized to each administration method and the number of participants assigned to each site of injection is desired to be balanced. Previous population PK analyses have shown that participants with a lower body weight tended to have a lower clearance, central volume of distribution, or both. While the

effects of body weight on these PK parameters were statistically significant, it was not considered to be clinically relevant. However, to mitigate these potentially confounding effects, weight is a stratification factor to ensure that an approximately equal number of participants in each weight category will be randomized to each reference and test administration methods.

A parallel-group design is chosen because a crossover design is impractical for mirikizumab, which has a half-life of approximately 9.3 days. Additionally, a crossover study could confound PK data if participants develop neutralizing anti-drug antibody.

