9.3.2.2. Pharmacokinetic Statistical Inference

The C_{max} , $AUC(0-\infty)$, and $AUC(0-t_{last})$ will be log-transformed and analyzed using a linear fixed-effects model. The model will include mirikizumab administration method ($2 \times 1\text{-mL SC}$ injections of 100 mg/mL citrate-free mirikizumab as reference, and $1 \times 2\text{-mL SC}$ injections of 100 mg/mL citrate-free mirikizumab as test), injection location, and weight category stratification as fixed effects. The administration method differences will be back-transformed to present the ratios of geometric least squares means and the corresponding 90% CI. Comparisons will be made between the 2 administration methods.

The 2 administration methods will be considered bioequivalent if the 90% CIs of the ratio of geometric least squares means fall within 0.80 to 1.25.

In addition, the t_{max} of mirikizumab between the administration methods will be analyzed using a Wilcoxon rank sum test. Estimates of the median difference, approximately 90% CIs, and p-values from the Wilcoxon rank sum test will be calculated.

Additional PK analyses may be conducted if deemed appropriate.

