9.5. Sample Size Determination

Approximately 484 participants, approximately 242 participants in each treatment arm, may be enrolled so that approximately 400 participants, 200 in each test and reference group, complete the study.

Within each weight category, participants will be assigned to an SC injection site of either the arm, thigh, or abdomen, approximately 80 participants per injection site for the reference and test arms.

A sample size of 200 participants per treatment group will provide approximately 90% probability that the 90% CI of the geometric mean ratio of C_{max} and AUC between groups will fall within the equivalence boundary of 0.80 to 1.25. This sample size calculation was based on the assumptions that the coefficient of variation of PK parameters is up to 41.8% for each treatment group and the expected ratio of geometric means is between 0.9 and 1.1.

10. Supporting Documentation and Operational Considerations

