4.2. Demography and Participant Dispositions

Participant disposition will be listed. The demographic variables age, sex, race, ethnicity, country of enrolment, site ID, body weight, weight category, height, and body mass index will be summarized by treatment, and overall; the data will also be listed. All other demographic variables will be listed only.

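### An inexpensive precision gain, not an error: the primary PK model adjusts for body weight only in three bands, and log Day -1 weight could be added before PK data are seen

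*SAP*

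**What the plan says.** SAP 4.3.2.1 models log Cmax, log AUC(0-∞) and log AUC(0-t_last) on administration method, "injection site location, and weight category stratification as fixed effects". In its example code the weight stratum is a CLASS variable. Protocol 9.3.2.2 gives the same model: administration method, "injection location, and weight category stratification as fixed effects". Neither document puts weight or BMI into the model as a continuous variable.

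The reason for adjusting is in Protocol 2.2.4: "Body weight was identified as a covariate on the clearance of mirikizumab and BMI was identified as a covariate on the SC bioavailability" of mirikizumab, in the direction of lower exposure in heavier people. It adds: "Although the effect size of weight or BMI is not considered clinically relevant, it represents a potential confounding factor for the bioequivalence evaluation". Protocol 4.2 gives the remedy: "to mitigate these potentially confounding effects, weight is a stratification factor".

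The bands are below 75.0, 75.0 to 85.0 and above 85.0 kg, set from Day -1 weight (Protocol 4.1). The number itself is collected: the Schedule of Activities notes "Only weight will be measured on D-1 and D71 or ED", and under SAP 4.2 "body weight, weight category, height, and body mass index will be summarized by treatment".

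Power is based on 200 completers per arm, a true ratio between 0.9 and 1.1, and the assumption that "the coefficient of variation of PK parameters is up to 41.8% for each treatment group" (Protocol 9.5; SAP 5 has the same assumptions).

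**The concern.** In a parallel single-dose study, variation between people sets the width of the 90% CI. Two of the three bands are open-ended, so the model treats a 50 kg and a 74 kg participant alike, and likewise an 86 kg and a 110 kg participant. If exposure keeps falling with weight inside a band, that part of the variation stays in the error term, although the value needed to remove it is measured on everyone before dosing.

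What is at stake is precision only. A narrower interval makes it slightly more likely that a truly equivalent device passes, most noticeably if the true ratio lies near 0.90, where the design has almost no margin above 90%.

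**Working it through.** **1. Reproduce the plan's power.** Inputs from Protocol 9.5 and SAP 5: 200 per arm, CV 41.8%, limits 0.80 to 1.25, 90% CI.
- Log-scale variance = ln(1 + 0.418²) = 0.1610; SD = 0.4013.
- Residual df = 400 − 6 = 394 (intercept 1, method 1, location 2, weight band 2).
- CI half-width on the log scale = 1.6487 × 0.4013 × √(2/200) = 0.0662, a factor of 1.068 either side.
- Power of the two one-sided tests: 90.1% at ratio 0.90, 99.6% at 0.95, 93.8% at 1.10. The stated figure of about 90% stands.

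**2. What the bands leave behind (assumed).** The documents give no weight distribution, so two were taken: N(78,13) and N(80,15) kg, limited to 45 to 130 kg and cut at 75 and 85 kg.
- Variance of log weight: 0.0278 and 0.0343.
- Share captured by the bands: 77% and 78%.
- Average within-band variance: 0.0065 and 0.0077. By band, low/middle/high, it is 0.0116/0.0013/0.0047 and 0.0133/0.0013/0.0067, so the remainder lies mostly in the open-ended bands.

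**3. Gain from log weight (assumed slope b, exposure proportional to weight^−b).** 41.8% is taken as the CV after banding.
- Gross variance removed = b² × within-band variance / 0.1610.
- Cost of estimating one more coefficient: the variance of the treatment difference is multiplied by 1 + 1/392.
- Example, b = 1.0: 0.0065/0.1610 = 4.0% gross; 0.960 × 1.00255 = 0.962, so 3.8% net; √0.962 = 0.981, so the CI is 1.9% narrower.

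| Slope b | Gross variance removed | Net of cost | CI narrower by | Power at 0.90 | Worth in completers (of 400) |
|---|---|---|---|---|---|
| 0 | 0 | −0.26% | −0.13% | 90.0% | about −1 |
| 0.5 | 1.0 / 1.2% | 0.8 / 0.9% | 0.4 / 0.5% | 90.3 / 90.3% | 3 / 4 |
| 0.75 | 2.3 / 2.7% | 2.0 / 2.4% | 1.0 / 1.2% | 90.6 / 90.7% | 8 / 10 |
| 1.0 | 4.0 / 4.8% | 3.8 / 4.5% | 1.9 / 2.3% | 91.0 / 91.2% | 16 / 19 |

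Paired entries are for N(78,13) / N(80,15). At ratio 1.10, power moves from 93.8% to between 93.9% and 94.6% for slopes 0.5 to 1.0.

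**4. Break-even.** Gain equals cost when b² × within-band variance / 0.1610 = 1/393, so b = √(0.1610 / (393 × 0.0065)) = 0.25, or 0.23 with 0.0077.

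**5. Sensitivity to the assumptions.**
- With log-weight SD of 0.14 to 0.22 around 79 kg and slopes 0.5 to 1.0, the CI narrows by 0.3% to 2.9% and power at 0.90 is 90.2% to 91.5% (variance inflation not charged).
- If 41.8% is the CV before any weight adjustment, the step from bands to continuous weight at ratio 0.90 is 90.9 to 91.1% and 91.1 to 91.4% (slope 0.5), or 93.3 to 94.2% and 94.1 to 95.1% (slope 1.0).

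**6. For scale.** At ratio 0.90, a CV of 40% gives 92.0% and 220 evaluable per arm gives 92.3%. Both exceed anything in the table.

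**The case against.** The strongest reply is that there is no defect here. The protocol names weight, stratifies on it and models the strata, and the bands already capture about 77% of log-weight variance under the assumed distributions. The benefit rests on a slope, a weight spread and a reading of 41.8% that the documents do not supply. Their only remark on effect size, that it is not clinically relevant, does not favour the upper slopes. The power gain is largest at the corner of the design: at ratio 0.95 power is 99.6% already, and an observed 0.95 with limits 0.889 to 1.015 would become 0.891 to 1.013 at best. SAP 4.3.1 allows weight-normalized parameters and SAP 4.3.2.1 allows further PK analyses. Altering the primary model of an open-label trial also takes a formal revision.

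Most of this stands. It makes the change optional and the benefit conditional. Two parts do not settle the matter. The optional analyses leave the primary model as it is. And the sentence that calls the effect not clinically relevant also calls it a potential confounder of this comparison.

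A reader might also infer more than the documents support:
- **That the ratio is biased or weight is uncontrolled.** Treatment is randomized within weight strata and the strata are in the model.
- **That BMI must be added because it is named.** Under assumed slopes of 0.25 to 0.5, log BMI as a second term yields 0.02% to 0.9% of residual variance net of its cost, or 0.01 to 0.2 power point. With both terms and no effect, power is 89.9%.
- **That correcting chance imbalance within bands is a further benefit.** It is the same gain as the variance reduction, since chance imbalance is already part of the standard error.

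**Conclusion.** The point holds as an optional improvement. The primary model is sound and the sample-size statement is correct. Adding log Day -1 weight might narrow the 90% CI by about 0.4% to 2.3% and raise power at ratio 0.90 from 90.1% to between 90.3% and 91.2%. This assumes slopes of 0.5 to 1.0, weights N(78,13) or N(80,15) kg, and 41.8% as the CV after banding. It would be going too far to say that the interval will narrow: below a slope of about 0.25 it does not, and the documents do not show where this population lies. The change would seldom alter a bioequivalence conclusion. The case for it is that the downside is smaller still and no new data are needed.

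**What to change.** If no PK data have been seen:
- Add log(Day -1 body weight) as one continuous covariate to the model in SAP 4.3.2.1, beside administration method, injection location and weight category. In the code this is one extra term that is not listed in CLASS.
- Leave the 0.80 to 1.25 rule unchanged and do not add BMI.
- Report the category-only model as a sensitivity analysis.
- State whether the exploratory comparisons by injection location, which reuse this model, also carry the covariate.
- Record the change in SAP 4.6, which at present reports none, and align Protocol 9.3.2.2.

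If PK data have been seen, keep the present primary model and use the continuous-weight model only as a sensitivity analysis. The documents do not show which situation applies.

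The statistical cost is one of 394 residual degrees of freedom and, if weight predicts nothing within bands, about 0.1 point of power and a CI 0.13% wider. The procedural cost is a dated SAP version, since SAP 1 requires the plan to be final before the first participant visit, and a matching protocol sentence. Both could ride on a revision made for other reasons, for example to bring the SAP's enrolment of 440 into line with the protocol's 484.

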
 To evaluate the bioequivalence of a 200-mg SC dose of 100 mg/mL citrate-free mirikizumab solution using a 1 × 2-mL AI (test) compared to using 2 × 1-mL AI (reference) 	
 C_{max}, $AUC(0-\infty)$, and $AUC(0-t_{last})$
Secondary	

 To describe the safety of a 200-mg SC dose of 100 mg/mL citrate-free mirikizumab solution using a 1 × 2-mL AI (test) compared to using 2 × 1-mL AI (reference) 	
 TEAEs and SAEs
Exploratory	

 To evaluate the impact of injection-site location on PK 	
 C_{max}, $AUC(0-\infty)$, and $AUC(0-t_{last})$

Abbreviations: AI = autoinjector; $AUC(0-\infty)$ = area under the concentration versus time curve from time zero to infinity; $AUC(0-t_{last})$ = area under the concentration versus time curve from time zero to time t , where t is the last time point with a measurable concentration; C_{max} = maximum observed drug concentration;

PK = pharmacokinetics; SAE = serious adverse event; SC = subcutaneous; TEAE = treatment-emergent adverse event.

4. Study Design

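### SAP 4.3.2.1 sets out to explore heterogeneity across injection sites but prespecifies no direct estimate of how the test/reference ratio differs between them (minor)

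*SAP*

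**What the plan says.** Protocol section 3 lists one exploratory objective: "To evaluate the impact of injection-site location on PK", with Cmax and the two AUCs as endpoints. Protocol 9.3.4.1 leaves the details of further exploratory analyses to the SAP.

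SAP 4.3.2.1 gives a primary model with main effects for administration method, location and weight category. Two sets of exploratory comparisons follow:

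- Test versus reference, "compared separately at each injection location (injection location will be removed from the model above").
- Arm versus abdomen and thigh versus abdomen, separately within each administration method, with administration dropped from the model.

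The SAP says these are not formal analyses but serve "rather to explore potential heterogeneity; therefore, bioequivalence will not be determined based on this exploratory purpose". The example code for the primary model contains "lsmeans administration / alpha=0.1 cl pdiff" and a matching statement for location. Pooled location contrasts are therefore produced, but they are not in the text's list of comparisons. The section also permits additional PK analyses, and SAP 4.3.2 adds PK summaries by treatment and site.

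**The concern.** Heterogeneity here means that the test/reference ratio differs between arm, thigh and abdomen. The quantity that measures it is a ratio of two site-specific ratios, with its interval. Separate fits give three ratios and three intervals but no prespecified estimate of any difference between them, so the reader is left to compare by eye.

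The question has substance. Under Protocol 6.1 the reference dose is split between two limbs or two abdominal quadrants, while the test dose is one 2-mL injection. A ratio that depends on site is conceivable, though this is an inference and not something the documents state.

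The location objective is also served less well than it could be. Every location comparison named in the text uses only half of the participants.

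**Working it through.** **Inputs.** Protocol 9.5 and SAP section 5 give the same planning assumptions. The power claim is "A sample size of 200 participants per treatment group will provide approximately 90% probability" for the interval criterion, under which the 90% CI must "fall within the equivalence boundary of 0.80 to 1.25". On variability, the plan assumes that "the coefficient of variation of PK parameters is up to 41.8% for each treatment group". On the size of the true effect, it takes it that "the expected ratio of geometric means is between 0.9 and 1.1". Both documents target 400 completers. An equal split over three sites gives 200/3, about 67 per arm per site, and 400/3, about 133 per site with arms pooled.

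**Reproducing the plan's figure.** Log-scale SD = sqrt(ln(1 + 0.418²)) = 0.4013. Two one-sided t-tests with 200 per arm give 90.1% power at a true ratio of 0.90 and 93.8% at 1.10. The stated figure of about 90% reproduces, so the same SD is used below.

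**Precision of a site-specific ratio.** SE = 0.4013 × sqrt(2/67) = 0.0693.

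**Precision of a between-site ratio-of-ratios.** The sites hold different participants, so SE = sqrt(0.0693² + 0.0693²) = 0.0981. The 90% CI half-width is 1.649 × 0.0981 = 0.162 on the log scale, a factor of exp(0.162) = 1.18 either way. If all 80 enrolled per arm per site were evaluable, the site SE would be 0.0634 and the factor exp(1.649 × 1.414 × 0.0634) = 1.16.

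**Precision of a location contrast.**
- Within one arm: SE = 0.4013 × sqrt(2/67) = 0.0693, 90% CI factor about 1.12.
- Arms pooled: SE = 0.4013 × sqrt(2/133) = 0.0492, 90% CI factor about 1.08.

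**Power of an administration-by-location test** (F test on 2 and 394 df, 67 per arm per site, two sites at ratio 1.00):

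| Third site | 5% level | 10% level |
|---|---|---|
| 0.90 | 18% | 28% |
| 0.85 | 38% | 51% |
| 0.80 | 65% | 76% |

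**How often would separate fits mislead?** Simulation with an identical true ratio at all three sites, 67 per arm per site:

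| Event | Ratio 1.00 | 0.95 | 0.90 |
|---|---|---|---|
| At least one site CI leaves 0.80–1.25, separate fits | 32% | 52% | 86% |
| Same, site ratios taken from one interaction model | 31% | 51% | 86% |
| At least two site CIs fail to overlap | 5% | 5% | 5% |
| At least one site CI excludes the mean of the three estimates | 11% | 11% | 11% |

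The first two rows reflect small numbers per site and a common ratio that may lie near the margin. The last two rows are signs of sites differing from each other. They occur about as often as a false signal from an interaction test at the 5% or 10% level.

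**The case against.** The strongest reply is that nothing of consequence is missing. The comparisons are declared informal and no bioequivalence decision by site will be made. The location objective concerns a location effect rather than an interaction, and the example code already outputs the pooled location contrasts. The site estimates come from disjoint participants, so anyone can form a ratio-of-ratios from them. Further PK analyses are allowed. Sites are assigned about equally within each arm, so the additive primary model in effect averages the site log-ratios even if they differ.

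All of this stands, and it is why the point is minor. It does not supply the missing item: a named, prespecified estimate of the quantity that the SAP says it wants to explore.

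Two stronger readings are tempting, and neither is supported. One is that chance alone will often make a site look different, on the strength of the 31–86% probability that some site's CI leaves 0.80–1.25. That probability concerns a decision by site that the SAP rules out. It hardly changes under the interaction model, and visible disagreement between sites arises in only about 5–11% of homogeneous trials. The other is that the trial as planned could not tell whether the ratio is constant. The planned outputs allow the contrast to be derived; it is just not prespecified.

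**Conclusion.** The point holds as a minor improvement to an exploratory analysis. The SAP states an aim of exploring heterogeneity but prespecifies no estimate of it, and its listed location comparisons give up precision (SE 0.069 against 0.049) that the pooled data would provide. The primary bioequivalence conclusion does not depend on it.

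The figures assume 67 completers per arm per site, an equal split across sites, the CV at its stated maximum of 41.8%, and no gain from adjusting for weight category. A lower CV or more evaluable participants would narrow every interval. Even so, a half-width of about a factor of 1.18 means that the trial can describe between-site differences only roughly, and the interaction test can easily miss a moderate one.

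**What to change.** Leave the primary model as it is. In SAP 4.3.2.1, add one exploratory model on the PK analysis set with administration, location, weight category and administration-by-location, and then:

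- Report the between-site ratios-of-ratios with 90% CIs as the main heterogeneity output, and take the site-specific ratios from the same model.
- Give the interaction test as secondary, with its limited power stated.
- Name the pooled arm-versus-abdomen and thigh-versus-abdomen contrasts, which the example code already produces, as the main answer on location. The within-method comparisons can stay as supporting detail.
- Keep the sentence that rules out bioequivalence decisions from these comparisons.

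The cost is one more model and a few lines of SAP text, with no new data. The downside is an extra exploratory output of limited precision. The text should say that a non-significant interaction is not proof of homogeneity.
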